## Definition of Worsening Heart Failure\*

### Presence of both:

#### I. New or progressive symptoms/signs of decompensation heart failure

- History
  - Significant weight gain
  - Worsening dyspnea
  - Worsening fatigue
- Physical Examination
  - Newly elevated jugular venous pressure
  - New cardiac S3 gallop rhythm
  - New pulmonary rales
  - New hepatic congestion
  - New peripheral edema
  - New development of cool extremities

#### II. Unplanned intensification of decongestive therapy in response to progressive symptoms/signs of heart failure:

- Oral
  - Increased dose of loop diuretic
  - Addition of thiazide diuretic to loop diuretic
- Intravenous administration of diuretic

\* Mallick et al. PROSPECT Trial. J Am Coll Cardiol HF 2016;4:749–55

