## 17.1.19 DEVICE THROMBUS

Device thrombus will be defined as any thrombus attached to or near an implanted valve and will be subclassified as:

- *Clinically significant valve thrombosis*: visualization of thrombus by echo or by MDCT (including HALT  $\geq 50\%$ ) and evidence of arterial embolism or new/worsening heart failure.
- *Significant thrombosis without clinical sequelae*: visualization of thrombus by echo or by MDCT (including HALT  $\geq 50\%$ ) in the absence of arterial embolism or new/worsening heart failure, meeting criteria of significant increase in mean gradient

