# The Early Feasibility Study of the Intrepid™ TMVR Transseptal System Clinical Investigation Plan

Version 4.0

Page 82 of 102

Medtronic

across the implant\* and warranting initiation or intensification of systemic anticoagulation.

- *Subclinical thrombosis*: visualization of thrombus by echo or by MDCT (including HALT  $\geq 50\%$ ) in the absence of arterial embolism or new/worsening heart failure and not meeting criteria of significant increase in mean gradient across the implant\*.

If thrombus is discovered on the implant at autopsy, it will be considered *clinically significant with clinical sequelae* if there was evidence of arterial embolism or new/worsening heart failure diagnosed ante- or postmortem. In the absence of arterial embolism or new/worsening diagnosed ante- or postmortem, thrombosis will be considered *significant without clinical sequelae* if last available echo met criteria of significant increase in mean gradient across the implant\* and *subclinical* if last available echo does not meet criteria of significant increase in mean gradient across the implant\*.

\*trans-mitral mean  $\Delta \geq 6$  mmHg AND  $\geq 5$  mmHg increase from discharge (10)

The definition of **Worsening Heart Failure** is related to the valve thrombosis events. For Heart Failure admissions, please refer to **Hospitalization** subclassified as Heart Failure.

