2. Examples of intravenous heart failure therapies contributing to this definition would include bolus or continuous infusion of loop diuretic agents; continuous infusion of vasodilators such as nitroglycerin, nitroprusside, or nesiritide; inotropic agents such as dobutamine; inodilators such as milrinone; beta agonists; and vasoconstrictors such as dopamine, epinephrine, and norepinephrine. Also included would be other invasive or mechanical heart failure treatments such as ultrafiltration, cardiac resynchronization therapy, and hemodynamic assist devices including intra-aortic balloon counterpulsation or left ventricular (LV) or biventricular assist devices. Treatment with intravenous antiarrhythmic medications or electrical cardioversion and/or ablation in the absence of other intravenous or invasive heart failure treatments would not per se constitute criteria for heart failure hospitalization (but would qualify as a cardiovascular hospitalization). Similarly, a heart failure exacerbation that can be managed solely by augmentation of oral heart failure therapies does not meet the pre-defined criteria for heart failure hospitalization.

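### The heart-failure test in EFS CIP 17.1.19 lists only diuretic steps, so a few severe valve thromboses can be filed below clinically significant

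*Combined protocol and SAP*

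**What the plan says.** References are to the early feasibility study (EFS) CIP, version 4.0, unless stated otherwise.

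- **17.1.19, thrombus classes.** A thrombus seen on echo or MDCT is *clinically significant* if there is also "evidence of arterial embolism or new/worsening heart failure". Without either, the class depends on the mean gradient (at least 6 mmHg, and at least 5 mmHg above discharge). If that criterion is met and anticoagulation is to be started or intensified, the class is *significant without clinical sequelae*. If it is not met, the class is *subclinical*.
- **17.1.19, worsening heart failure box.** The section ties this definition to the thrombosis events and sends heart failure admissions to 17.1.25. The box asks for "Presence of both" of two limbs: I, "New or progressive symptoms/signs of decompensation heart failure"; and II, "Unplanned intensification of decongestive therapy in response to progressive symptoms/signs of heart failure". Limb II lists "Increased dose of loop diuretic", "Addition of thiazide diuretic to loop diuretic" and intravenous diuretic, with nothing to mark these as examples.
- **17.1.19, autopsy rule.** For a thrombus found at autopsy: "In the absence of arterial embolism or new/worsening diagnosed ante- or postmortem, thrombosis will be considered" one of the two lower classes, chosen by the gradient on the last available echo.
- **17.1.25, note 2.** For heart failure hospitalization, the qualifying intravenous therapies include diuretics, vasodilators, inotropes and vasoconstrictors. The note goes on: "Also included would be other invasive or mechanical heart failure treatments such as ultrafiltration, cardiac resynchronization therapy, and hemodynamic assist devices".

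**The concern.** The top thrombus class should collect the thromboses that harmed the subject. Without embolism, entry depends on a diuretic change, which is a marker of congestion and not of harm in general. A subject with worse fatigue and a higher oral diuretic dose enters the top class. A subject who collapses, is supported with inotropes or a pump, or goes straight to valve reintervention need not. The same admission could count as a heart failure hospitalization under 17.1.25 and still not be worsening heart failure under 17.1.19.

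At stake is how the severity of one device complication is reported. Section 4.1.1 makes the nature, severity and frequency of complications the primary objective, and section 13.0 sends event summaries for every subject to FDA.

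**Working it through.** The plan states no figure here to reproduce. The check is to write the rule out and see what decides the class.

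**Step 1. The rule (17.1.19).**

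- Worsening heart failure = limb I AND limb II.
- Clinically significant = embolism OR worsening heart failure.
- Significant without clinical sequelae = neither of these, AND gradient met, AND anticoagulation warranted.
- Subclinical = neither of these, AND gradient not met.

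**Step 2. Apply it** to a subject with thrombus, heart failure symptoms or signs (limb I met) and no arterial embolism.

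| Listed diuretic step | Gradient criterion | Anticoagulation warranted | Class |
|---|---|---|---|
| No | Not met | Either | Subclinical |
| No | Met | Yes | Significant without clinical sequelae |
| No | Met | No | No class fits |
| Yes | Either | Either | Clinically significant |

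Shock, inotropes, assist devices, reintervention and death are not inputs. In this setting the diuretic step alone separates the top class from the rest. In a sudden death without preceding signs, limb I may fail as well.

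**Step 3. Compare with other definitions in Appendix 17.1.**

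| Complication | What raises its grade |
|---|---|
| Air embolism (17.1.21) | Haemodynamic instability or respiratory failure, among others |
| Device fracture (17.1.17) | Device failure, recurrent symptoms or reintervention |
| LVOT obstruction (17.1.27) | Death or explant (intraprocedural cases); septal reduction therapy |
| Paravalvular leak (17.1.35) | Intervention or surgery, among others |
| Pericardial effusion (17.1.36) | Tamponade, intervention or hospitalization |
| Valve thrombus (17.1.19) | Embolism, or heart failure with a diuretic step |

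Cardiogenic shock (17.1.11) and valve-related reintervention, for which thrombosis is a named example (17.1.38), are defined but not linked to the thrombus class.

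**Step 4. The autopsy rule.** It accepts heart failure diagnosed before or after death. Limb II, however, requires a treatment change made in life in response to symptoms, so a purely post-mortem diagnosis cannot satisfy the box as written. The fallback is the last echo, which may predate the fatal thrombus.

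**Step 5. Size.** Section 8.2 gives n = 45 at most. One reclassified case shifts the proportion by 1/45 = 2.2 percentage points. Exact (Clopper-Pearson) 95% limits are the 0.025 quantile of Beta(x, n − x + 1) and the 0.975 quantile of Beta(x + 1, n − x). For x = 0 the upper limit is 1 − 0.025^(1/45) = 7.9%.

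| Cases (assumed) | Proportion | 95% limits |
|---|---|---|
| 0/45 | 0% | 0 to 7.9% |
| 1/45 | 2.2% | 0.06 to 11.8% |
| 2/45 | 4.4% | 0.5 to 15.1% |

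The documents give no number of such cases; 0 to 2 is an assumption made for scale.

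**The case against.** Four points against the concern carry weight.

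- **The CEC has some room.** The class text says new or worsening heart failure, but only worsening is defined. The CEC could treat *new* heart failure as a separate route, although limb I already covers new signs. The post-mortem wording gives room in deaths. Ultrafiltration, or a first loop diuretic, could also be read into limb II. This stands in part, but it does not cover inotropes, assist devices, reintervention or death as such. The CEC charter, which might settle it, is not among the documents.
- **Overlap is large.** Intravenous loop diuretic is the first therapy named in 17.1.25 note 2, and it satisfies limb II. Most decompensated subjects would probably receive it. That is a clinical assumption, but a reasonable one. The exposed cases are rapid collapse, diuretics withheld, immediate reintervention and sudden death.
- **The separation is deliberate.** 17.1.19 says its definition serves thrombosis events and cites a published trial for it. The difference from 17.1.25 is therefore a signposted choice, though one with a gap.
- **Nothing disappears.** Shock, reintervention and death have their own definitions, the events remain reportable as SAEs, and every subject is reviewed individually. This stands in full.

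A reader might infer that the primary endpoint is biased. The documents do not support that: it counts implant, delivery or device related SAEs through 30 days (4.2.1) and does not use the thrombus class. Nor is any endpoint in 4.2.2 or 4.2.3 expressed through it. The SAP in the file does count a major device thrombosis as a device failure (7.9.3). That SAP belongs to the transapical pilot study (CIP-1403), and its major/minor grading is not mapped to these three classes.

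**Conclusion.** The gap is real on the wording of 17.1.19: a thrombus with grave consequences, no embolism and no diuretic step can be placed in a class whose name says there were no clinical sequelae, or in the subclinical class. The autopsy rule has the same weakness and does not fit limb II.

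Its reach is narrow. The effect is on the reported severity of device thrombosis, at 2.2 points per case if all 45 subjects are enrolled and treated. The assumed range of 0 to 2 cases includes no effect. Two stronger readings fail: that the worst thromboses are routinely placed in the milder classes, and that deaths are always excluded from the top class. The overlap in therapies and the post-mortem wording both count against them. Priority is low, and the change is optional.

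**What to change.** In 17.1.19 and the CEC charter, keep the present routes and add that a thrombus is also *clinically significant* when the CEC attributes any of these to it:

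- (a) heart failure treated with intravenous or mechanical haemodynamic therapy of the kind listed in 17.1.25 note 2, excluding cardiac resynchronization, or a primary (class IA) heart failure hospitalization;
- (b) cardiogenic shock as defined in 17.1.11;
- (c) valve reintervention or reoperation for symptoms or haemodynamic compromise;
- (d) death.

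Apply the same list in the autopsy rule, and reconcile its post-mortem wording with limb II.

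The causal link is needed. Without it, secondary (class IB, noncardiac) heart failure admissions would count. Thrombolysis alone should not count either, because it would raise an asymptomatic, gradient-only thrombus to the top class.

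This changes classification only, not patient care. The cost is wording in two documents, the usual amendment approvals (15.7), a causal attribution by the CEC, and a second look at any thrombus already classed. Section 11.1 already requires treatment given for an adverse event to be reported; the CRFs are not in the file, so the sponsor should confirm that they capture what is needed. The clinically significant thrombosis rate can only stay the same or rise.

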## 17.1.20 EMBOLISM (BLOOD CLOT)

- Free flowing blood clot or lesion material that is located in the systemic or pulmonary circulation that occurs in the absence of infection after the immediate perioperative period. Embolism may be manifested by a neurological event or a noncerebral embolic event.

## 17.1.21 EMBOLISM (AIR)

*Venous air embolism* – a subset of gas embolism that occurs when gas is introduced into the venous system.

*Arterial air embolism* – a subset of gas embolism that occurs when gas is introduced into the arterial system.

- Symptomatic = With Clinical Sequelae – (e.g. signs and/or symptoms of hemodynamic instability, ischemia, respiratory failure and/or new neurologic deficit)
- Asymptomatic = Without clinical sequelae

## 17.1.22 ENCEPHALOPATHY

Altered mental state (e.g., seizures, delirium, confusion, hallucinations, dementia, coma, psychiatric episode, etc.).

## 17.1.23 ENDOCARDITIS

Endocarditis will be defined and classified according to the Mitral Valve Academic Research Consortium (MVARC); Clinical Trial Design Principles and Endpoint Definitions for Transcatheter Mitral Valve Repair and Replacement: Part 2: Endpoint Definitions; JACC, 2015 (14).

Any 1 of the following:

- Fulfillment of the modified Duke endocarditis criteria (described below), or
- Evidence of abscess, paravalvular leak, pus, or vegetation confirmed as secondary to infection by histological or bacteriological studies during an operation or autopsy.

Should be further subclassified by organism, and early (<1 yr) vs. late (≥1 yr)

Modified Duke Criteria
Definite endocarditis according to the Modified Duke Criteria includes: 

• Histologic and/or microbiologic evidence of infection at surgery or autopsy, or

• 2 major criteria, or

• 1 major criteria or 3 minor criteria, or

• 5 minor criteria

 Major and minor criteria are as follows:

# The Early Feasibility Study of the Intrepid™ TMVR Transseptal System Clinical Investigation Plan

Version 4.0

Page 84 of 102

Medtronic

## Modified Duke Criteria

### Major Criteria

- Blood cultures positive for Infective Endocarditis (IE)
  - Typical microorganisms consistent with IE isolated from two separate blood cultures, as noted below
    - Viridans streptococci, Streptococcus bovis, Staphylococcus aureus, or HACEK group
    - Community-acquired enterococci in the presence of a primary focus
  - Microorganisms consistent with IE isolated from persistently positive blood cultures defined as:
    - At least two positive cultures or blood samples obtained >12 hours apart, or
    - All of three, or a majority of four or more separate cultures of blood, the first and last sample obtained > one hour apart
  - Single blood culture positive for Coxiella burnetti or an antiphase I IgG antibody titer >1:800
- Evidence of endocardial involvement
  - Positive results of echocardiography for IE defined as:
    - Oscillating intracardiac mass on a valve or supporting structures in the path of regurgitant jets or on implanted material in the absence of an anatomic explanation, or
    - Abscess, or
    - New partial dehiscence of a valvular prosthesis

New valvular regurgitation (worsening or changing or pre-existing murmur not sufficient)

### Minor Criteria

- Predisposition: predisposing heart condition or intravenous drug use
- Fever: temperature >38°C
- Vascular phenomena: major arterial emboli, septic pulmonary infarcts, mycotic aneurysm, intracranial hemorrhage, conjunctival hemorrhages, and Janeway's lesions
- Immunological phenomena: glomerulonephritis, Osler's nodes, Roth's spots, and rheumatoid factor
- Microbiological evidence: positive blood culture but does not meet a major criterion (as noted above) or serological evidence of active infection with organism consistent with infectious endocarditis.
- Echocardiographic findings: consistent with IE but do not meet a major criterion as noted above

### Modified Duke Criteria

If only 1 major and 1-2 minor criteria are fulfilled, or if only 3-4 minor criteria are fulfilled, the event will be coded as "possible endocarditis"

Medtronic Business Restricted

**CONFIDENTIAL**

056-F275, vC Clinical Investigation Plan Template

## 17.1.24 HEMOLYSIS

Hemolysis will be defined and classified according to the Mitral Valve Academic Research Consortium (MVARC); Clinical Trial Design Principles and Endpoint Definitions for Transcatheter Mitral Valve Repair and Replacement: Part 2: Endpoint Definitions; JACC, 2015 (14). The presence of anemia requiring transfusion plus decreased/absent haptoglobin and/or increased LDH levels; recommended, but not required, to be confirmed by a hematologist.

- Hemolysis will be further sub-classified to the following:
  - Hemolysis with PVL: The presence of anemia requiring transfusion plus decreased/absent haptoglobin and/or increased LDH levels and evidence of a Paravalvular leak on transesophageal or transthoracic echocardiography
  - Hemolysis without PVL: The presence of anemia requiring transfusion plus decreased haptoglobin/absent and/or increased LDH levels and no evidence of a Paravalvular leak on transesophageal or transthoracic echocardiography
    - (e.g. hemolysis due to other devices such as Impella, etc. would fall into this category)

## 17.1.25 HOSPITALIZATION

Hospitalization will be defined and classified according to the Mitral Valve Academic Research Consortium (MVARC); Clinical Trial Design Principles and Endpoint Definitions for Transcatheter Mitral Valve Repair and Replacement: Part 2: Endpoint Definitions; JACC, 2015 (14).

Heart Failure hospitalization will be defined and classified according to MVARC.

Definition and Classification of Hospitalization (or Rehospitalization)	
Definition	Hospitalization is defined as admission to an inpatient unit or ward in the hospital for $\geq 24$ h, including an emergency department stay. Hospitalizations planned for pre-existing conditions are excluded unless there is worsening of the baseline condition.
Hospitalization is further subclassified as:	

# The Early Feasibility Study of the Intrepid™ TMVR Transseptal System Clinical Investigation Plan

Version 4.0

Page 86 of 102

Medtronic

## Definition and Classification of Hospitalization (or Rehospitalization)

- I. Heart failure hospitalization: Both of the following additional criteria are present:
  - Symptoms, signs and/or laboratory evidence of worsening heart failure
  - Administration of intravenous or mechanical heart failure therapiesPatients hospitalized with heart failure are further subclassified as:
  - IA. Primary (cardiac related) heart failure hospitalization
  - IB. Secondary (noncardiac related) heart failure hospitalization
- II. Other cardiovascular hospitalization: such as for coronary artery disease, acute myocardial infarction, hypertension, cardiac arrhythmias, cardiomegaly, pericardial effusion, atherosclerosis, stroke, or peripheral vascular disease without qualifying heart failure
- III. Non-cardiovascular hospitalization: not due to heart failure or other cardiovascular causes, as defined above

1. The diagnosis of worsening heart failure is on the basis of: 1) symptoms of worsening heart failure such as increased dyspnea, orthopnea, paroxysmal nocturnal dyspnea, fatigue, decreased exercise tolerance, and/or history of weight gain; 2) physical examination evidence of worsening heart failure such as neck vein distention, the presence of a third heart sound, pulmonary rales, ascites or pedal edema, and/or hypotension or signs of worsening end-organ perfusion; and/or 3) diagnostic evidence of worsening heart failure such as radiographic pulmonary congestion, natriuretic peptide levels greater than the upper limit of normal in the absence of conditions known to affect these values (e.g., renal dysfunction, infection), arterial oxygen desaturation or increasing oxygen requirements, and/or acidosis. No single finding is necessarily diagnostic, and adjudication by the clinical events committee should be on the basis of all available clinical evidence, guided by the specifics of the protocol definition.
2. Examples of intravenous heart failure therapies contributing to this definition would include bolus or continuous infusion of loop diuretic agents; continuous infusion of vasodilators such as nitroglycerin, nitroprusside, or nesiritide; inotropic agents such as dobutamine; inodilators such as milrinone; beta agonists; and vasoconstrictors such as dopamine, epinephrine, and norepinephrine. Also included would be other invasive or mechanical heart failure treatments such as ultrafiltration, cardiac resynchronization therapy, and hemodynamic assist devices including intra-aortic balloon counterpulsation or left ventricular (LV) or biventricular assist devices. Treatment with intravenous antiarrhythmic medications or electrical cardioversion and/or ablation in the absence of other intravenous or invasive heart failure treatments would not per se constitute criteria for heart failure hospitalization (but would qualify as a cardiovascular hospitalization). Similarly, a heart failure exacerbation that can be managed solely by augmentation of oral heart failure therapies does not meet the pre-defined criteria for heart failure hospitalization.

### 17.1.26 IATROGENIC ATRIAL SEPTAL DEFECT

Iatrogenic ASD will be defined and classified according to the Mitral Valve Academic Research Consortium (MVARC); Clinical Trial Design Principles and Endpoint Definitions for Transcatheter Mitral Valve Repair and Replacement: Part 2: Endpoint Definitions; JACC, 2015 (14).

- Major: significant left-to-right shunt ( $Qp:Qs \geq 2:1$ ) or symptomatic requiring the need for closure
- Minor: nonsignificant shunt that is still present at  $\geq 6$  months

Medtronic Business Restricted

**CONFIDENTIAL**

056-F275, vC Clinical Investigation Plan Template

### 17.1.27 INTERACTION WITH NON-MITRAL VALVE INTRACARDIAC STRUCTURES

Interaction with non-mitral- valve intracardiac structures will be classified as

- Left ventricular outflow tract obstruction:
  - Visual narrowing of the LVOT tract AND
  - Peak LVOT jet velocity  $\geq 2.7$  m/s (peak instantaneous gradient  $\geq 30$  mmHg) measured by CW Doppler under basal (resting) conditions or physiologically provoked (Valsalva maneuver or post premature ventricular contraction) AND
  - An increment in peak LVOT gradient  $\geq 10$  mm Hg from baseline
  - Additional notes and considerations:
    - LVOT obstruction will be considered severe if peak LVOT jet velocity  $\geq 3.5$  m/s (peak instantaneous gradient  $\geq 50$  mm Hg).
    - **Non-severe:** Peak LVOT jet velocity greater than or equal to 2.7 ms/s to 3.4 m/s (peak instantaneous gradient  $\geq 30$  mm Hg)
    - **Non-event:** Less than 2.7 m/s peak LVOT jet velocity
    - All cases with peak LVOT jet velocity  $\geq 2.7$  m/s (peak instantaneous gradient  $\geq 30$  mm Hg) measured by CW Doppler will be submitted to the CEC for adjudication.
    - AEs/SAEs related to *intraprocedural* increase in LVOT gradient will be submitted to the CEC for adjudication. Cases of intraprocedural LVOTO resulting into death or explant will be considered severe LVOTO.
    - Cases of LVOTO resulting into septal reduction therapy (alcohol septal ablation or septal myectomy) will be considered severe LVOTO.
    - Cases of LVOTO incidentally discovered by pathology will be assessed based on the last available peak LVOT jet velocity measured by CW Doppler; any attempt should be done to submit this last echo to the Echo Core Lab and to the CEC. Alternatively, the last follow-up echo Core Lab CW measurements will be used to define LVOTO.

Outflow Tract Gradient Severity Scale CW Doppler			
	Mild	Moderate	Severe
Velocity m/sec	$\geq 2.7$ -3.1	3.2 - 3.4	$\geq 3.5$
Peak Gradient mmHg	$\geq 30$ -39	40 - 49	$\geq 50$

- Aortic valve regurgitation ( $\geq$  moderate or 2+)
- Other

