## **4.0 Objectives and Endpoints**

### **4.1 Objectives**

#### **4.1.1 Primary Objective**

The primary objective of the study is to evaluate the safety of the Intrepid™ TMVR System by assessing the nature, severity and frequency of complications associated with the delivery and/or implantation of the device.

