## 12.0 Data Review Committees

### 12.1 Clinical Events Committee Review

An independent Clinical Events Committee (CEC) will review and adjudicate, at a minimum, all deaths and primary endpoint related adverse events. The CEC will consist of, at a minimum: an interventional cardiologist, a cardiothoracic surgeon, an echocardiologist and a heart failure specialist who are not participants in the trial. Additional specialists, such as neurologists, may also be selected as part of the CEC.

The purpose of the CEC is to conduct a medical review and classify/adjudicate, at a minimum, all deaths and/or clinical endpoints collected in the trial according to definitions and processes outlined in the trial protocol and the CEC charter, which will be developed and approved by Medtronic and the CEC members. Safety endpoint results will be based on CEC adjudication.

All applicable events will be reviewed and adjudicated by a minimum of three CEC members. All other events will be reviewed and assessed by qualified internal Medtronic safety individual(s) to ensure that adjudication by the CEC is not required and that the events are appropriately classified by the investigator.

Prior to event adjudication, the CEC will draft a charter, in collaboration with Medtronic, to establish explicit rules outlining the minimum amount of data required and the algorithm followed in order to classify/adjudicate a trial endpoint related clinical event. CEC decisions will be documented in meeting minutes, which will be maintained in the trial master file and adjudication results will be recorded in the trial database.

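### In CIP 17.1.27, death or explant makes LVOT obstruction severe only if the obstruction was intraprocedural, so a later-arising fatal or explanted case at 2.7–3.4 m/s is graded non-severe

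*Combined protocol and SAP*

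**What the plan says.** Section 17.1.27 of the Early Feasibility Study CIP calls a case LVOTO when three conditions hold together: narrowing is seen, peak CW Doppler velocity is at least 2.7 m/s (resting or provoked), and the peak gradient has risen by at least 10 mmHg from baseline. Severity then follows velocity.

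- Severe: "LVOT obstruction will be considered severe if peak LVOT jet velocity" is 3.5 m/s or more, paired with 50 mmHg.
- Non-severe: "Peak LVOT jet velocity greater than or equal to 2.7 ms/s to 3.4 m/s". The scale in the same section divides this band into mild (2.7–3.1) and moderate (3.2–3.4).
- Non-event: "Less than 2.7 m/s peak LVOT jet velocity".

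Two lines override velocity because of what happened to the subject:

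- Death or explant: "Cases of intraprocedural LVOTO resulting into death or explant will be considered severe LVOTO".
- Septal reduction: "Cases of LVOTO resulting into septal reduction therapy (alcohol septal ablation or septal myectomy) will be considered severe LVOTO".

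A further line deals with findings at pathology: "Cases of LVOTO incidentally discovered by pathology will be assessed based on the last available peak LVOT jet velocity measured by CW Doppler".

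Under CIP 12.1, "An independent Clinical Events Committee (CEC) will review and adjudicate, at a minimum, all deaths and primary endpoint related adverse events". The committee works from the protocol definitions and from its own charter, which is not among the documents. The primary objective in CIP 4.1.1 is pursued by "assessing the nature, severity and frequency of complications associated with the delivery and/or implantation of the device".

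**The concern.** The two outcome rules do not match. A case that ends in septal reduction is severe whenever the obstruction arose. A case that ends in death or explant is severe only if the obstruction was intraprocedural. For obstruction that develops or is first recognised afterwards, death and explant add nothing to the grade, and velocity alone decides it.

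This is out of line with how the same appendix treats other complications. Cardiac perforation is major if it results in death or needs unplanned intervention (17.1.1 and 17.1.8). Device fracture is major if it requires reintervention (17.1.17), and pericardial effusion is major if it requires intervention (17.1.36). Thrombus found at autopsy is judged first on its clinical sequelae (17.1.19). None of these upgrades depends on the event having begun during the procedure.

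Severity is one of the three things the primary objective sets out to describe, and compatibility with the outflow tract is named in the secondary objective (4.1.2). Where the mismatch bites, it lowers the recorded grade, which favours the device.

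**Working it through.** The plan gives no figure to reproduce here, so the check is to apply the text of 17.1.27 line by line.

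**Inputs, all from 17.1.27.** Velocity cuts of 2.7, 3.2 and 3.5 m/s; the death/explant line, limited to intraprocedural obstruction; the septal-reduction line, with no limit.

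**Grades for a case that meets the LVOTO definition:**

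| When the obstruction arose or was found | Outcome | 2.9 m/s | 3.3 m/s | 3.6 m/s |
|---|---|---|---|---|
| During the procedure | Death or explant, at any later time | severe | severe | severe |
| After the procedure | Death or explant | non-severe (mild) | non-severe (moderate) | severe |
| Either | Septal reduction | severe | severe | severe |
| Either | No consequence | non-severe (mild) | non-severe (moderate) | severe |

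The second and fourth rows are identical. The gap is confined to post-procedural obstruction at 2.7–3.4 m/s with no septal reduction.

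**Could the gradient column rescue such a case?** With the simplified Bernoulli relation, gradient = 4v²:

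- 2.7 m/s: 4 × 7.29 = 29.2 mmHg
- 3.1 m/s: 4 × 9.61 = 38.4 mmHg
- 3.2 m/s: 4 × 10.24 = 41.0 mmHg
- 3.4 m/s: 4 × 11.56 = 46.2 mmHg
- 3.5 m/s: 4 × 12.25 = 49.0 mmHg

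These agree closely with the printed gradient cuts of 30, 39, 40, 49 and 50 mmHg. The gradient restates the velocity and gives no separate route to severe.

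**Below 2.7 m/s.** The text does not say whether an outcome rule or the non-event line governs. A case below the floor does not meet the LVOTO definition at all, so this is an unresolved conflict and not only a question of grade. The pathology line has a similar problem: it relies on the last available velocity and does not say what happens if the CEC links the obstruction to the death.

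**Size.** The documents give no rate of post-procedural LVOTO, so the number of affected cases cannot be estimated. With 45 treated subjects, one case is 1/45 = 2.2 percentage points. The exact 95% interval is 0–7.9% for 0/45 and 0.1–11.8% for 1/45. These figures are for scale only, because the plan does not promise a severe-LVOTO proportion.

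**The case against.** **The timing word qualifies the obstruction, not the outcome.** This stands, and it sets the scope of the point. A reader might infer that any obstruction that kills or forces explant after the subject leaves the procedure room escapes the rule. The sentence does not say that. An obstruction created at deployment that causes death on day 2 still fits it.

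**The limit may have a purpose.** The sentence completes a bullet about events linked to a gradient rise during the procedure, when a standard CW Doppler grade may be missing. Later echocardiograms are scheduled and read by the core lab. This explains the wording but does not justify the difference from the septal-reduction line. The end-of-procedure TEE list in 9.9.1 does not name LVOT velocity, and the first scheduled post-implant TTE is at discharge or by 14 days (9.10). A subject who dies or is explanted before then may have no scheduled post-implant velocity.

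**Nothing is hidden.** This also stands. A reader might infer that fatal obstructions drop out of the safety results, or that the plan ranks death below a rescue procedure. The documents support neither. A related death or explant within 30 days counts in the primary endpoint (4.2.1) whatever its LVOTO grade, and collection of serious adverse events continues to study exit. The CEC adjudicates all deaths. Mortality and reoperation have their own classifications (17.1.32, 17.1.38). Each subject is reviewed individually, with event summaries to FDA (13.0). LVOT patency has no severity tier in CIP 4.2.2, nor in section 7.9.2 of the only SAP supplied, which belongs to the transapical Pilot Study.

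**The charter may already cover this.** It may. It was not available, and the CEC also applies the protocol text, so a charter rule cannot be assumed to close the gap.

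A reader might add that low output depresses velocity in exactly these subjects. The documents give no flow data and allow provoked measurements, so the point does not rest on that.

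**Conclusion.** The inconsistency is in the text and should be corrected, within narrow limits. It affects LVOTO that arises or is first found after the procedure, measures 2.7–3.4 m/s, has no septal reduction, and is adjudicated as causing death or explant. Such a case is recorded as non-severe, as if it had no clinical consequence. The consequence is an under-graded severity description under the primary objective. Endpoint counts do not change, because no stated endpoint separates severe from non-severe LVOTO.

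The conclusion rests on two readings: that the timing word in the death/explant line describes the obstruction, and that no charter rule fills the gap. How often the situation would occur is unknown. In a study of at most 45 treated subjects, even one such case would be prominent in any severity summary.

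**What to change.** In 17.1.27, remove the timing limit from the death/explant line so that it matches the septal-reduction line. For example: LVOTO at any time, during or after the procedure, that the CEC adjudicates as resulting in death or explant is classified as severe.

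In the same edit, state which rule governs when the CEC finds causation but (a) the measured velocity is below 2.7 m/s, or (b) the obstruction was found at pathology and only an earlier velocity exists. Letting the outcome rule prevail in (a) would change which cases count as LVOTO events as well as their grade, so that choice needs to be explicit. Carry the wording into the CEC charter. Leave the core-lab echo definition of LVOT patency as it is, so that the performance endpoint is unaffected.

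The cost is one amended sentence, a short statement of precedence and a charter update. Any case already adjudicated would need to be re-read against the new wording. No new data are needed and patient care does not change. The one consequence for the sponsor is that the severe-LVOTO count can only stay the same or rise.
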